8.2 Extent of Exposure

Time on treatment (weeks) will be calculated as (date of last dose of study drug – date first dose of study drug + 1)/7. Time on treatment will be summarized by treatment group for each period using descriptive statistics for all subjects in the safety population.

The date and time of the first and last dose of each study period will be presented in a data listing for all subjects in the safety population.

8.3 Adverse Events

Adverse events will be coded using the Medical Dictionary for Regulatory Activities (MedDRA) Version 21.1 to identify the system organ class and preferred term.

Adverse events that occur or are reported to worsen in severity on or after date of first dose of study treatment in period 1 will be considered to be TEAEs.

TEAEs will be categorized as occurring in either study period 1 or study period 2 according to the following rules:

- Adverse events that occur or are reported to worsen in severity on or after date and time of start of period 1 study treatment and on or before date and time of end of period 1 study treatment will be attributed to study period 1. Adverse events that occur or are reported to worsen in severity on the start date of period 1 study treatment that do not have a time associated with the event will be attributed to study period 1.
- Adverse events that occur or are reported to worsen in severity after the end date of period 1 study treatment and on or before the date of end of period 2 study treatment will be attributed to study period 2. Adverse events that occur or are reported to worsen in severity on the date of end of period 2 study treatment that do not have a time associated with the event will be attributed to study period 2.

- Adverse events that occur on the crossover date between study period 1 and study period 2 that do not have a time associated with the event will be attributed to study period 1.
- Adverse events that occur in both study period 1 and study period 2 will be attributed to both study periods.

TEAEs that occurred after the subject's last study period will be classified as follow-up TEAEs. If a subject entered both the first and second study periods, any event occurring after the end date of the second study period will be considered a follow-up TEAE. If a subject discontinued prior to the start of the second study period, any event occurring after the end date of the first study period will be considered a follow-up TEAE.

TEAEs will be summarized for all subjects in the safety population. TEAEs will be summarized by treatment group. The total number of TEAEs occurring will be shown. The number and percentage of subjects experiencing any TEAE will also be provided. In addition, summary tables will reflect a count and percentage of subjects experiencing at least 1 TEAE in each system organ class and preferred term. All percentages will use the number of subjects in the safety population as the denominator. Therefore, if a subject has more than 1 AE within a system organ class, the subject will be counted only once in that system organ class. If a subject has more than 1 AE that codes to the same preferred term, the subject will be counted only once for that preferred term. Tabular summaries will be sorted by descending frequency by system organ class and by preferred term in the MS1819 treatment group.

Treatment-emergent AEs will be presented by treatment group and overall with percentages that use the number of subjects in the safety population as the denominator.

Treatment-emergent AEs will also be summarized by maximum relationship to study drug and maximum severity. Relationship to each study treatment (MS1819-SD and prestudy PERT) will be scored as Related or Unrelated. Severity will be rated as Mild, Moderate, or Severe. All percentages will use the number of safety subjects as the denominator. Summary tables will reflect a count and percentage of subjects experiencing at least 1 TEAE in each system organ class, preferred term and grouping, relationship, or severity. If a subject experiences more than 1 AE within a system organ class or preferred term, that subject will be counted only once for that event under the maximum severity or most related category for the study drug. Similarly, in the event that relationship or severity data are missing, the study analysis will follow the assumption of maximum relationship or severity in the summary tables. These summaries will be presented by treatment group and overall with percentages that use the number of subjects in the safety population as the denominator. The tabular summaries will be sorted by descending frequency by system organ class and by preferred term in the MS1819 treatment group.

All AEs will be presented in data listings for subjects in the safety population.

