1. PURPOSE OF THE ANALYSES

The statistical analysis plan (SAP) is being developed after review of the AzurRx Biopharma, Inc. (AzurRx), protocol number AZ-CF2001, but before any analyses of the data. The SAP contains detailed information to aid in the implementation of the statistical analyses and reporting of the study data for use in the clinical study report (CSR). This SAP is being written with due consideration of the recommendations outlined in the most recent International Conference on Harmonisation (ICH) E9 Guideline entitled Guidance for Industry: Statistical Principles for Clinical Trials and the most recent ICH E3 Guideline, entitled Guidance for Industry: Structure and Content of Clinical Study Reports.

This SAP describes the analysis sets that will be analyzed, the subject characteristics parameters, the efficacy parameters, and the safety parameters that will be evaluated. The details of the specific statistical methods that will be used will be provided in this SAP. If differences occur between analyses described in the SAP and the current protocol, those found in this SAP will assume primacy. If additional analyses are required to supplement the planned analyses described in this SAP, they may be completed and will be identified in the CSR. Table and listing specifications are provided in a separate document.

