4.3 Safety Population

The safety population, which will be used for all safety analyses unless stated otherwise, will include all randomized subjects who receive at least 1 dose of treatment. Subjects in the safety population will be analyzed according to the actual treatment received regardless of their randomized assignment.

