8. SAFETY EVALUATION

8.1 Overview of Safety Analysis Methods

All safety analyses will be performed using the safety population and summarized by actual treatment (MS1819-SD regardless of period vs. PERT regardless of period) allowing direct intrasubject comparison of the tolerability of MS1819-SD vs. PERT. Safety measures summarized will include AEs, laboratory data, vital signs, and concomitant medications. Additionally, exposure to study treatment during the study will be displayed.

Safety data will not be imputed, except for partial and missing dates, which will be imputed only for defining treatment-emergent AEs (TEAEs) and concomitant medications. Imputed dates will not be presented in data listings.

TEAEs will be defined as any AEs that occur or are reported to worsen in severity on or after the date of first dose of study treatment in period 1. Partial dates will be imputed for the purposes of defining TEAEs as follows:

- For a missing start day where the month and year are present, the start day will be set to the first day of the month, unless 1) the first day of the month is before the date of first dose of study treatment and the month and year are the same as the month and year of the date of first dose of study treatment, and 2) the end date is on or after the date of first dose of study treatment or the end date is completely missing, in which case the start day will be set to the first day of first dose of study treatment.
- For a missing start day and month where the year is present, the start day and month will be set to January 1st, unless 1) January 1st is before the date of first dose of study treatment and the year is the same as the year of the date of first dose of study treatment, and 2) the end date is on or after the date of first dose of study treatment or the end date is completely missing, in which case the start day and month will be set to that of the date of first dose of study treatment.
- For a missing end day where the month and year are present, the end day will be set to the last day of the month, unless the month and year are the same as the month and year of the last contact date for the subject, in which case the end day will be set to that of the subject's last contact date.

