8.4 Deaths, Serious Adverse Events, and Other Significant Adverse Events

Treatment-emergent SAEs, TEAEs leading to study discontinuation, TEAEs resulting in death, treatment-emergent SAEs by relatedness, treatment-emergent SAEs leading to discontinuation, and treatment-emergent SAEs resulting in death will be summarized for all subjects in the safety population. Summary tables will reflect a count and percentage of subjects experiencing at least 1 TEAE in each system organ class and preferred term within each AE subset (serious, leading to discontinuation, death). These summaries will be presented by treatment group and overall with percentages that use the number of subjects in the safety population as the denominator. These tabular summaries will be sorted by descending frequency by system organ class and by preferred term in the MS1819 treatment group.

Adverse events leading to study discontinuation, AEs resulting in death, and SAEs will be presented in data listings for subjects in the safety population.

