8.6.3 Other Safety Measures

8.6.3.1 Prior and Concomitant Medications

The prior and concomitant medications will be coded using the latest version of World Health Organization Drug Dictionary (WHO Drug) Global Version (September 2018) to identify the drug class and preferred drug name.

Concomitant medications will include all medications that started on or after day of first dose of the study treatment in the first period or that stopped on or after day of first dose of study treatment in the first period. Prior medications will include all medications that started and stopped prior to the day of first dose of the study treatment in the first study period.

Concomitant medications will be categorized as occurring in study period 1 or study period 2. Concomitant medications that started or stopped on or after day of first dose of study treatment in period 1 and before the start of period 2 are attributed to period 1. Concomitant medications that started prior to the first dose of study treatment in period 1 and stopped on or after day of first dose of study treatment in period 1, or are ongoing, are attributed to period 1. Concomitant medications that started or stopped on or after day of first dose of study treatment in period 2 are attributed to period 2. Concomitant medications that started prior to the study and are stopped on or after day of first dose of study treatment in period 2, or are ongoing, are attributed to period 2.

The number and percentage of subjects using prior and concomitant medications will be tabulated for each study period by Anatomical Therapeutic Chemical (ATC) level 1 term, ATC level 2 term, and preferred drug name for all subjects in the safety population. If a subject has more than 1 medication within an ATC level 1 term, the subject will be counted only once in that ATC level 1 term. Similarly, if a subject has more than 1 medication within an ATC level 2 term, the subject will be counted only once in that ATC level 2 term. If a subject has more than 1 medication that codes to the same preferred drug name, the subject will be counted only once for that preferred drug name. All percentages will use the number of subjects in the safety population as the denominator. The tabular summary will be sorted by descending frequency by ATC level 1 term, ATC level 2 term, and preferred drug name.

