Prior medications will be summarized overall by planned treatment sequence. Concomitant medications will be presented by actual treatment group and overall with percentages that use the number of subjects in the safety population as the denominator. Prior and concomitant medication data will also be presented in a data listing for subjects in the safety population.

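### As written, safety percentages by treatment divide by the whole safety population rather than by those who took the treatment, and a timed event late on the switch day fits neither period

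*SAP*

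**What the plan says.** **Denominator.** The safety population "will include all randomized subjects who receive at least 1 dose of treatment" (SAP 4.3); exposure to both treatments is not required. Safety results are "summarized by actual treatment (MS1819-SD regardless of period vs. PERT regardless of period" (SAP 8.1). The denominator is then stated table by table:

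- SAP 8.3, treatment-emergent adverse events (TEAEs): "presented by treatment group and overall with percentages that use the number of subjects in the safety population as the denominator".
- SAP 8.4, serious events, discontinuations and deaths: "These summaries will be presented by treatment group and overall with percentages that use the number of subjects in the safety population as the denominator".
- SAP 8.6.3.1, by treatment: "Concomitant medications will be presented by actual treatment group and overall with percentages that use the number of subjects in the safety population".
- SAP 8.6.3.1, by period: "prior and concomitant medications will be tabulated for each study period", with the rule "All percentages will use the number of subjects in the safety population as the denominator".

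SAP 1 adds: "Table and listing specifications are provided in a separate document".

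**Period attribution (SAP 8.3).** Period 1 closes at the date and clock time at which its treatment ends. Period 2 opens only after the calendar date on which Period 1 treatment ends. Events on the crossover date that carry no time go to Period 1. Nothing is said about crossover-date events that do carry a time.

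**The concern.** In a parallel-group trial each patient sits in one treatment column, so naming the safety population as the denominator does no harm. In this crossover a completer sits in both columns and a patient who stops before Period 2 in only one. SAP 8.3 itself foresees such patients. Read literally, they stay in the denominator of a treatment they never took, and that column's percentage is too low. If such losses differ between sequences, the comparison of MS1819 with PERT is distorted as well.

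The attribution gap matters because the columns are by treatment: an event with no period has no treatment column. Protocol 8.3 has patients switch as soon as the second marker stool has been collected, so the first dose of the new treatment can fall on the date the old one ends.

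Safety is a primary objective (SAP 2.1.1) and the sample size was chosen mainly for it (SAP 2.6). These tables are its main display by treatment.

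**Working it through.** **Denominator**

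Inputs: 30 completers, 20% dropout and 38 patients (SAP 2.6); 1:1 allocation (SAP 2.5); at least 15 completers per sequence (SAP 2.2). The plan does not say how many patients will stop before Period 2, or from which sequence, so I show the range. I assume that all 38 are dosed, 19 per sequence.

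1. The plan's own figure: 30 / (1 − 0.20) = 37.5, rounded up to 38. It reproduces.
2. Largest loss per sequence within the plan: 19 − 15 = 4.
3. Let a be the PERT-first patients and b the MS1819-first patients who stop before Period 2. Then 38 − a take MS1819 and 38 − b take PERT.
4. Printed rate / true rate = number exposed / 38:

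| Losses before Period 2 (a / b) | MS1819 column | PERT column |
|---|---|---|
| 0 / 0 | 38/38 = 1.000 | 38/38 = 1.000 |
| 2 / 2 | 36/38 = 0.947 | 36/38 = 0.947 |
| 4 / 4 | 34/38 = 0.895 | 34/38 = 0.895 |
| 4 / 0 | 34/38 = 0.895 | 38/38 = 1.000 |
| 0 / 4 | 38/38 = 1.000 | 34/38 = 0.895 |

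For example, 6 patients with an event on MS1819 are 6/38 = 15.8% as written, but 6/34 = 17.6% of those exposed when a = 4.

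5. If the true rate p is the same on both treatments, the false gap is p × |a − b| / 38. With a 4/0 split this is 10% × 4/38 = 1.1 points, 20% × 4/38 = 2.1 points, or 40% × 4/38 = 4.2 points. A 4/4 split gives no gap. Stopping after the first Period 2 dose causes no error.
6. For concomitant medications by period, the losses of both sequences fall on the Period 2 column: (38 − a − b)/38, which is 30/38 = 0.789 at 4/4. The Period 1 column is unaffected. That table contrasts periods, not treatments.

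**Attribution**

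Suppose Period 1 treatment ends at 09:00 and the first Period 2 dose is at 12:00 on the same date. Applying the SAP 8.3 rules literally:

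| Event | Period under SAP 8.3 |
|---|---|
| 08:00 that day | 1 |
| No time, that day | 1 |
| 10:00 that day | none |
| 15:00 that day | none |
| 23:59 that day | none |
| Next day | 2 |

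The 15:00 and 23:59 events follow the first dose of the new treatment and still have no period.

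A similar mismatch exists at the start. SAP 8.1 and 8.3 count an event as treatment-emergent from the date of first dose, but Period 1 opens at a date and time. A timed Day 1 event before the first dose is therefore a TEAE with no period.

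**The case against.** **A per-treatment N is implied.** SAP 4.3 and 8.1 sort subjects by treatment actually received, and a patient who never took MS1819 has no place in its column. This is a fair reading of intent, and the table specifications, which are not available here, may already follow it. But the SAP gives one denominator for the treatment columns and the overall column in the same sentence, and nowhere states a second one.

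**The consequences are small.** This stands. Safety is assessed descriptively (Protocol 10.6). Counts are printed beside percentages (SAP 3), the exposure summary gives the number on each treatment (SAP 8.2 with SAP 3), and withdrawals are shown by period and sequence (SAP 5.1). A reader can recompute the rates.

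**The distortion could be much larger.** A reader might infer this by letting 8 losses split 6/2 or 8/0 between sequences. With 19 per sequence, that leaves 13 or 11 completers in one sequence, below the planned 15. For the treatment columns, errors beyond those tabulated require the plan's own minimum to be missed.

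**Timed events are meant to be placed by their time.** A tie-break for untimed events does suggest this, but the Period 2 rule as written excludes the rest of that date. The gap is narrow all the same: it concerns some hours of one day, and Protocol 9.2 asks for onset dates without mentioning times.

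**Patients who stop in Period 1 seem to have the same gap.** A reader might infer this from the sentence that starts follow-up after the end date. The more general sentence before it in SAP 8.3 classes any TEAE after the last study period as follow-up, which reasonably covers them.

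**Conclusion.** Both points hold on the text, as minor corrections.

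- **Denominator.** With 38 dosed, 19 per sequence and at least 15 completers in each, a treatment column prints between 1.000 and 0.895 of the true rate. The false gap at equal true rates is at most 1.1, 2.1 or 4.2 points at a true 10%, 20% or 40%. It can favour either treatment, depending on which sequence loses patients, and there is no error if nobody stops before Period 2. The documents do not support saying that the final tables will be wrong, because the table specifications may already use the exposed N.
- **Attribution.** A timed event on the date Period 1 treatment ends, after its end time, has no period and so no treatment column. It remains a TEAE, is listed and counts in the overall column. How many such events to expect cannot be estimated from the documents.

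Neither point touches the efficacy analysis.

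**What to change.** 1. **SAP 8.3, 8.4 and 8.6.3.1.** For each treatment column, use the safety subjects with at least one dose of that treatment. For tabulations by period, use those dosed in that period. Keep the full safety population for the overall column. Check the table shells and align them.
2. **SAP 8.3.** Add one rule for patients who enter Period 2: a timed event on the date Period 1 treatment ends, after its end time, goes to Period 1 if it precedes the first Period 2 dose and to Period 2 if it occurs at or after that dose. In the example above, 10:00 goes to Period 1, and 15:00 and 23:59 go to Period 2. Leave the rule for later dates and the Period 1 tie-break for untimed crossover-date events as they are. Redefining the whole boundary by first Period 2 dose would move events that already have a period: with a first dose at 08:00 the day after Period 1 ends, an event at 06:00 that day would shift from Period 2 to Period 1.
3. **SAP 8.1 and 8.3.** Start treatment emergence and Period 1 at the same point, by date and time when a time is recorded, so that a timed Day 1 event before the first dose is not a TEAE without a period.

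The cost is SAP wording and table shells. First and last dose dates and times for each period are already to be listed (SAP 8.2), so no new data are needed.

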8.4 Deaths, Serious Adverse Events, and Other Significant Adverse Events

Treatment-emergent SAEs, TEAEs leading to study discontinuation, TEAEs resulting in death, treatment-emergent SAEs by relatedness, treatment-emergent SAEs leading to discontinuation, and treatment-emergent SAEs resulting in death will be summarized for all subjects in the safety population. Summary tables will reflect a count and percentage of subjects experiencing at least 1 TEAE in each system organ class and preferred term within each AE subset (serious, leading to discontinuation, death). These summaries will be presented by treatment group and overall with percentages that use the number of subjects in the safety population as the denominator. These tabular summaries will be sorted by descending frequency by system organ class and by preferred term in the MS1819 treatment group.

Adverse events leading to study discontinuation, AEs resulting in death, and SAEs will be presented in data listings for subjects in the safety population.

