#### 7.3.4 Removal of Patients from the Study

A patient may be withdrawn from the study at any time for any of the following reasons:

- Loss to follow-up
- Withdrawal of consent, for any reason, at any time
- Major protocol deviations that could compromise the interpretation of the results
- Occurrence of an immunoallergic reaction
- Occurrence of an adverse reaction (ie, an SAE related to IMP) that justifies the discontinuation of the IMP
- Pregnancy

The date of withdrawal and the reason for withdrawal must be fully documented in the case report form (CRF) and a short narrative description should be added in the patient's medical records.

If at the time of withdrawal, the patient has received the investigational study product (partially or totally), study staff should encourage the patient to attend the Early Withdrawal

---

Visit for follow-up safety investigations. These patients will be included in the ITT efficacy analysis and safety analysis.

If the reason for discontinuation is an AE, then the Investigator will seek to obtain follow-up information and to document the event until its resolution or stabilization. In any case, the Investigator will take all necessary measures to ensure the patient's safety and ensure the patient is treated in accordance with local standard of care.

If a patient is lost to follow-up, then the Investigator should make every effort to obtain maximum information on the reasons for the nonattendance to the visit and on the patient's state of health. All attempts will be documented in the patient's medical records.

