## 9.2 Reporting Procedures for All Adverse Events

AEs will be recorded in the CRF for all patients from the time the patient signs the informed consent form through the end of the study or patient withdrawal.

The Investigator is responsible for ensuring that all AEs (as defined in [Section 9.1](#) and as further specified below) observed by the Investigator or reported by patients are collected and recorded in the patients' medical records, in the CRF, and as an SAE in the electronic data capture system. These AEs will include the following:

1. All SAEs (as defined in [Section 9.1.2](#)) that occur.
2. All nonserious AEs (as defined in [Section 9.1.1](#)) that occur.

The following AE attributes must be assigned by the Investigator:

- AE diagnosis or syndrome(s) (if known, signs or symptoms if not known);
- event description (with detail appropriate to the event);
- dates of onset and resolution; severity; assessment of relatedness to study drug; and
- action taken with study medication.

The Investigator may be asked to provide follow-up information, discharge summaries, and extracts from medical records or CRFs.

It will be left to the Investigator's clinical judgment to determine whether the relatedness of an AE, and of sufficient severity to require the patient's removal from treatment or from the study. A patient may also voluntarily withdraw from treatment because of what he or she perceives as an intolerable AE. If either of these situations arises, the patient should be strongly encouraged to complete the End-of-Therapy assessments and be under medical supervision until symptoms cease or the condition becomes stable.

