9.2 Analysis Methods

9.2.1 Primary Efficacy Analyses

The primary efficacy endpoint is the CFA assessed at the end of each 3-week treatment period (Visit 6 or Visit 9). CFA is evaluated by the 72-hour marker-to-marker stool sample collection (1 measure at Visit 6 and 1 at Visit 9) and standardized high-fat diet during each supervised confinement. Coefficient of fat absorption represents the percentage of fat absorbed from the diet by the subject and is calculated from the results of the quantitative fecal fat measurement in conjunction with the dietary fat intake.

CFA will be calculated by using 2 data points:

- Fat consumption in grams as provided by the qualified dietitian at each site.
- Fat excretion in grams/24h as provided by the central laboratory.

CFA will be calculated as follows:

$$\frac{(\text{Grams/24h of fat consumed} - \text{Grams/24h of fat excreted}) \times 100}{\text{Grams/24h of fat consumed}}$$

The primary efficacy endpoint analysis will use the mITT population and be analyzed as randomized. For the analysis of CFA, if a subject switches study treatments (i.e. MS1819 to PERT or PERT to MS1819) during the confinement period, prior to the end of the stool collection, then the CFA value during that confinement period will be excluded from the analysis. The primary method for the analysis of the primary efficacy endpoint will be based on a mixed model. Missing CFA values will not be imputed.

The mixed model will include terms for sequence (MS1819-PERT, PERT-MS1819), random patient nested in sequence, period (1, 2), treatment (MS1819, PERT), and gastric acid suppression use (Y, N). The mixed model will be implemented using SAS® Proc MIXED, as shown in the model code below. The DDFM=KR option denotes the Kenward-Roger method for the denominator degrees of freedom. The variable GASTFL in the code below is the gastric acid suppression use flag (Y, N).

```
PROC MIXED;  
  CLASS SUBJECT SEQUENCE PERIOD TREATMENT GASTFL;  
  MODEL CFA = SEQUENCE TREATMENT PERIOD GASTFL /  
    DDFM=KR;  
  RANDOM SUBJECT(SEQUENCE);  
  LSMEANS TREATMENT / CL DIFF;  
  RUN;
```

The 95% CI of the difference in CFA for MS1819-SD minus CFA for porcine PERT will be used to assess the primary objective. Non-inferiority of MS1819-SD to porcine PERT is achieved if the lower bound of the 95% CI of the difference is greater than -15%,

where 15% is the non-inferiority margin. If non-inferiority is achieved, then superiority will be tested.

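### SAP 8.4 reports adverse events leading to study discontinuation but not those leading to stopping study treatment, so a patient who stops MS1819 for an adverse event and stays in the trial is absent from that table and listing

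*SAP*

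**What the plan says.** The primary safety objective (protocol 6.1, SAP 2.1.1) is the safety and tolerability of MS1819-SD at 2240 mg/day.

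SAP 8.4 sets out the adverse-event subsets to be summarised by treatment group:

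- For all treatment-emergent events, the subsets include "Treatment-emergent SAEs, TEAEs leading to study discontinuation, TEAEs resulting in death".
- For serious events, they include "treatment-emergent SAEs leading to discontinuation, and treatment-emergent SAEs resulting in death". Here the word discontinuation stands alone.
- For the listings: "Adverse events leading to study discontinuation, AEs resulting in death, and SAEs will be presented in data listings".

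No item refers expressly to events that led to stopping study treatment.

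Protocol 9.2 leaves it to the investigator to judge whether an event is "of sufficient severity to require the patient's removal from treatment or from the study". It adds: "A patient may also voluntarily withdraw from treatment because of what he or she perceives as an intolerable AE". The same section requires the investigator to record, for each adverse event, the action taken with study medication.

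**The concern.** How often a treatment has to be stopped because of adverse events is one of the most direct summaries of tolerability, and tolerability is part of the primary safety objective. SAP 2.6 also says that the sample size was selected mainly for safety.

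In this crossover, stopping the drug need not mean leaving the study. Every patient has their own porcine PERT. It is the comparator, and it is also the treatment that protocol 9.7 tells patients taken off study drug to resume. Someone who cannot tolerate MS1819 can stop it and still attend later visits. A table built on study discontinuation answers a narrower question than the objective asks, and a reader who takes it as the count of MS1819 stopped for adverse events may read too low a figure.

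**Working it through.** The point concerns which events are tabulated, so the main check is to trace a patient through the planned outputs. Take a patient who stops MS1819 for a non-serious, non-allergic adverse event, remains in the study and attends through Visit 10.

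1. **Protocol 7.3.4.** The reasons for withdrawal from the study that rest on an adverse event are an immunoallergic reaction and "Occurrence of an adverse reaction (ie, an SAE related to IMP) that justifies the discontinuation of the IMP". This patient meets neither, so that section does not by itself take them out of the study.
2. **SAP 8.4.** The patient did not discontinue the study and had no serious event. Read literally, they enter neither the discontinuation table nor the listing.
3. **SAP 8.3.** The event is counted by system organ class, preferred term, severity and relationship, and it is listed. No summary described there says that it led to stopping the drug.
4. **SAP 5.1.** If the stop is recorded as withdrawal from the treatment period, it is counted with its reason, by sequence. Sequence and period together identify the drug, but no preferred term is given. Completion is defined as reaching Visit 6 or Visit 9, so a patient who stops the drug but attends that visit may be recorded as completing the period.
5. **SAP 7.** Compliance divides capsules used by the days from first to last dose. A patient who takes full doses and then stops early scores about 100%.
6. **SAP 8.2.** Time on treatment is shorter, but no reason is attached.

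No described output therefore links the event term to the stopping of MS1819 for this patient.

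**Scale.** The documents give no rate of stopping, so the figures below only show how much one patient counts for.

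The plan's own figure comes first. Protocol 10.2 and SAP 2.6 say that an event not seen among 30 patients has an interval from 0% to 10%. The rule of three gives 3/30 = 10.0%. The one-sided exact 95% bound is 1 − 0.05^(1/30) = 9.5%. Either matches the stated 10%. The two-sided exact (Clopper-Pearson) upper limit is 1 − 0.025^(1/30) = 11.6%.

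For one event in n patients, the two-sided upper limit is the 97.5th percentile of Beta(2, n − 1).

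| n | One patient | Upper limit, 0 shown | Upper limit, 1 shown |
|---|---|---|---|
| 30 | 1/30 = 3.3% | 11.6% | 17.2% |
| 38 | 1/38 = 2.6% | 9.3% | 13.8% |

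As an illustration, assume that 4 of 38 patients stop MS1819 for an adverse event, a number that is not in the documents. The 8.4 table would show 4/38 = 10.5% if all four left the study, 2/38 = 5.3% if two stayed, and 0/38 = 0% if all stayed.

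**The case against.** The strongest reply is that little is lost:

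- SAP 8.3 keeps the event, with its severity and relationship.
- SAP 5.1 reports period withdrawals with reasons.
- The serious-event item in SAP 8.4 does not contain the word study, so part of the problem may be loose wording.
- Under protocol 7.3.4 a related serious event that justifies stopping the drug is itself a possible reason for study withdrawal. Consent may also be withdrawn for any reason, so a non-serious event can end participation too.
- The documents describe no standard path in which a patient stops MS1819 mid-period, takes PERT and completes every visit. The planned crossover comes only at the end of Visit 6.
- The table and listing specifications are separate attachments that are not available here, and they may add such a display.

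Most of this stands, and it narrows the point. A reader might infer that the patient vanishes from all tolerability output; SAP 8.3 and 5.1 show otherwise. A reader might also cite the SAP 9.2.1 rule that applies "if a subject switches study treatments (i.e. MS1819 to PERT or PERT to MS1819) during the confinement period" as evidence that stops for adverse events are expected. That rule covers switches in either direction, mentions no adverse event and applies only during confinement, so it does not support that reading.

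A further limit is that protocol 9.1.1 sends worsening of pancreatic insufficiency to its own form and does not count it as an adverse event unless it is serious. An added table based on adverse events would not capture stops for that reason either.

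The replies do not remove the gap itself. Protocol 9.2 foresees withdrawal from treatment for an adverse event as something other than removal from the study, and the SAP text calls for no table or listing of the events that cause it.

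**Conclusion.** The point holds in a limited form. SAP 8.4 as written leaves out of its discontinuation table and listing a patient who stops MS1819 for an adverse event, mainly a non-serious one, but stays in the study. It also uses the word discontinuation without saying of what. Other outputs keep the event, or in some cases the stop, but none described in the SAP ties the two together by preferred term.

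The number of patients affected cannot be known from the documents. Each one is worth 3.3 percentage points of 30 or 2.6 of 38; the four-patient illustration rests wholly on assumed figures.

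It is tempting to conclude that the omission favours MS1819, because PERT is the fallback and patients enter stable on it. That is plausible, but the documents give no stopping rates for either treatment, so the direction is an assumption and not a finding. Sample size, power and the primary efficacy analysis are not affected.

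**What to change.** In SAP 8.4:

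- Define discontinuation, and say at each use whether it means of study treatment or of the study.
- Add one table and one listing of treatment-emergent adverse events leading to discontinuation of study treatment, by the treatment being taken at onset. Derive them from the action-taken field that protocol 9.2 requires.
- Keep study discontinuation as a separate row.

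Before finalising, check that the response options for that field identify a permanent stop and the treatment concerned; the documents do not show them.

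The cost is one extra table and listing from a field already required, with matching edits to the display specifications. The sponsor must also accept that the MS1819 tolerability figure may look less favourable.
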